#### 5.3.7 Primary Patency

The time interval for primary patency is defined as the time from HD AV access creation to the first one of the following events: access thrombosis; any facilitation or maintenance intervention intended to support maturation or cannulation, as well as those to maintain, or re-establish functionality; access abandonment.

The failure for primary patency will be identified for the first occurrence of one of the followings:

- Access thrombosis: on the Post-Procedure Intervention page, Type is checked as "Thrombosis"; or on the
  Core Lab Analysis Duplex Ultrasound: EndoAVF Arm page, and Type is checked as "Thrombosis";
  Note: if the result from the Core Lab Analysis Duplex Ultrasound: EndoAVF Arm page is not available,
  use the corresponding information from the Duplex Ultrasound: EndoAVF Arm to determine Thrombosis.
- Intervention: on the Post-Procedure Intervention page, Date of Post Procedure Intervention is not NULL, and Type of Intervention is checked as "Facilitation Support AVF Cannulation", and/or "Facilitation Support AVF Maturation" and/or "Maintenance";
- Access Abandonment (Permanent Abandonment): on the EndoAVF Abandonment page, Date of
  Abandonment is not NULL, and the question of "All Possible Attempts Have Been Made to Improve the
  Condition of the Access" is checked as Yes, and the question of "Could Further Endovascular
  Interventions Salvage the Access" is checked as No, and the question of "Could Further Surgical
  Revisions Salvage the Access?" is checked as No, and Reason for Abandonment is selected as "The
  Access is No Longer Viable" or "The Access is Viable but there are Complications that Require the
  Abandonment of the Access".

Kaplan-Meier (KM) analysis will be used to estimate the time interval of primary patency. The following definition will be applied:

- If any failure event(s) as described above occurs, the participant is considered as having the event (loss of primary patency), and the first failure event date will be used in the analysis.
- If the participant was as transferred to PD, or had a kidney transplant, or had access discontinuation, or discontinued before the end of a specific visit window (e.g., 180+30 = Day 210 for 6-month visit) without the event, the participant is considered as censored the earliest date among these events (i.e., PD start date, kidney transplant date, date of access discontinuation, last date of available study data including the unscheduled visit date).

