- Otherwise, if the participant did not have any failure event and has passed a specific visit by the cutoff date of database lock, the participant will be censored at the end of the reporting time window (e.g., 180+30 = Day 210 for the 6-month reporting, 730+30 = 760 for the final 24-month reporting) for this analysis.

This endpoint will be evaluated on the AT population. The number of participants with events, number of participants censored, time to event (days), and proportion of participants with event free along with the 95% CI will be presented at 30-days, 6-weeks, 3-, 6-, 12-, 18-, and 24-months post creation using the KM method.

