#### **5.3.8** Cumulative Patency

The time interval for cumulative patency is defined as the time from HD AV access creation to access abandonment.

Kaplan-Meier (KM) analysis will be used to estimate the time interval of cumulative patency. The following definition will be applied:

- If permanent abandonment (as detailed in Section 5.2.4) occurs, the participant is considered as having the event (loss of cumulative patency), and the corresponding abandonment date will be used in the analysis.
- If the participant was as transferred to PD, or had a kidney transplant, or had access discontinuation, or discontinued before the end of a specific visit window (e.g., Day 210 for 6-month visit) without the event, the participant is considered as censored at the earliest date among these events (i.e., PD start date, kidney

transplant date, date of access discontinuation, last date of available study data including the unscheduled visit date).

• Otherwise, if the participant is still in the investigation without the event and has passed a specific visit by the cutoff date of database lock, the participant will be censored at the end of the reporting time window (e.g., 180+30 = Day 210 for the 6-month reporting, 730+30 = 760 for the 24-month reporting) for this analysis.

This endpoint will be evaluated on the AT population. The number of participants with events, number of participants censored, time to event (days), and proportion of participants with event free along with the 95% CI will be presented at 6-, 12-, 18-, and 24-months post creation using the KM method.

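### In the 6-month report, SAP 5.3.7 and 5.3.10.1 count events at any date but censor event-free participants at Day 210, so the literal Kaplan-Meier event-free estimates after Day 210 run toward zero (exploratory endpoints)

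*SAP*

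**What the plan says.** **Primary patency (SAP 5.3.7).**
- Event rule: "If any failure event(s) as described above occurs, the participant is considered as having the event (loss of primary patency"), dated at the first failure. The intervention component requires only that "Date of Post Procedure Intervention is not NULL, and Type of Intervention is checked as" one of the facilitation or maintenance categories. Neither statement has an upper time limit.
- Event-free participants who have passed the visit: "the participant will be censored at the end of the reporting time window", given as Day 210 (180 + 30) for the 6-month report and Day 760 for the final report.
- Earlier censoring applies to participants who move to PD, are transplanted, have access discontinuation, "or discontinued before the end of a specific visit window (e.g., 180+30 = Day 210 for 6-month visit) without the event".
- Output: event counts, censored counts and event-free proportions, "presented at 30-days, 6-weeks, 3-, 6-, 12-, 18-, and 24-months post creation using the KM method". The list is not divided between the two reports.

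**Time to CVC removal (SAP 5.3.10.1).** Any removal is an event on its date. Participants who still have the catheter are censored at Day 210 for the 6-month report. Evaluation times run to 24 months.

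**Related sections.**
- Cumulative patency (5.3.8) uses the same Day 210 censoring and lists 6, 12, 18 and 24 months, but defines its event by reference: "If permanent abandonment (as detailed in Section 5.2.4) occurs, the participant is considered as having the event (loss of cumulative patency"). Section 5.2.4 requires the abandonment date to fall within a specific visit, for example 395 days for 12 months.
- Functional maturation (5.3.4) and functional HD usability (5.3.5) accept events up to the database-lock cutoff and censor non-events at Day 210. They do state that the 6-month report shows the rate up to Day 210.
- The supportive safety analysis (5.1.1) and primary functional patency (5.3.9) put the same upper limit on events as on event-free status.

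**The concern.** The 6-month report is triggered when the last active treated participant completes 6 months (SAP 2.5). Enrollment is expected to take about 18 months (CIP Section 3). At that cut, participants therefore have roughly 6 to 24 months of potential follow-up, and some failures after Day 210 will be in the database.

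Kaplan-Meier requires that leaving the risk set carries no information about the coming event. Here it carries all of it. Of two participants both patent on Day 210, the one who later fails stays at risk until failing, and the one who stays patent is removed on Day 210. The late part of the curve then reflects the rule and not the fistula.

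The direction differs by endpoint. Late primary patency would look much worse than it is. For CVC removal, the event-free state is a catheter still in place, so the proportion removed would be pushed toward 100%. At stake are the late exploratory values in the 6-month report, together with event and censored counts that do not share a horizon.

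**Working it through.** **1. Is there follow-up beyond Day 210 at the 6-month cut?** The plan's own figure is more than 100 PY from 150 treated participants (CIP 7.3, SAP 2.4).
- Retention R(t): piecewise exponential through 1, 0.8, 0.6 and 0.4 at 0, 6, 12 and 24 months, from the stated attrition of 20%, 40% and 60%.
- Enrollment: uniform over 18 months (547.5 days), so potential follow-up f runs from c to c + 547.5 days, with the cut c = 180 to 210 days after the last index procedure.
- PY = 150 × mean over f of ∫₀ᶠ R(t) dt / 365.25 = 137 (c = 180) to 144 (c = 210). The plan's figure is reproduced.
- R(210) = 0.8 × 0.75^(27.5/182.5) = 0.766. The expected number still in the study past Day 210 is 150 × 0.766 × the share with f > 210 (0.945 to 1.0) = 109 to 115, before patency failures are removed.

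**2. What the literal rule does.** Let m be the number of failures observed after Day 210. Just after Day 210 the risk set is exactly those m participants, and none of them is later censored. For t > 210:

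S(t) = S(210) × (late failures occurring after t) / m.

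The curve therefore reaches exactly 0 at the last recorded failure. One late failure is enough (m = 1), whatever the true patency.

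**3. Size for primary patency.** Simulation: N = 150, 2,000 runs, enrollment and attrition as above, cut 180 days after the last enrollment. Failure times are Weibull, anchored at 72.4% at 6 months (CIP 2.1.2). The shape is an assumption: 1 (constant hazard) or 0.6 (falling hazard).

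| Mean KM estimate | Day 180 | Day 210 | 12 mo | 18 mo | 24 mo |
|---|---|---|---|---|---|
| Shape 1, literal rule | 72.7% | 68.9% | 23.5% | 4.1% | 0% |
| Shape 1, actual follow-up | 72.7% | 68.9% | 52.4% | 38.1% | 29.0% |
| Shape 0.6, literal rule | 72.7% | 70.5% | 23.7% | 4.3% | 0% |
| Shape 0.6, actual follow-up | 72.7% | 70.5% | 61.4% | 53.8% | 48.5% |

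The 24-month values with actual follow-up carry the last estimate forward at the edge of follow-up. The 12-month gap is 52.4 − 23.5 = 28.9 points and 61.4 − 23.7 = 37.7 points. The formula in step 2 shows why the literal 12-month value hardly depends on shape: 23.5/68.9 = 0.34 and 23.7/70.5 = 0.34, so about a third of the late failures seen by the cut come after 12 months in both cases.

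Estimates at or before Day 210 were identical in every run. Capping both events and non-events at Day 210 also leaves them unchanged.

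**4. Event counts.**
- Shape 1: 62.2 events, 41.3 by Day 210 and 20.9 later (20.9/62.2 = 34%).
- Shape 0.6: 51.9 events, 40.5 by Day 210 and 11.4 later (11.4/51.9 = 22%).

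**5. Sensitivity.** Raising the anchor to 77.3% (the cumulative patency figure in CIP 2.1.2, used only as a higher level) with shapes 1, 0.5 and 0.3 gives 26% to 27% at 12 months under the literal rule, against 60% to 73% with actual follow-up. Late failures then number about 4 to 19.

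No figure was computed for CVC removal. The algebra in step 2 applies there unchanged.

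**The case against.** The best defense is that a reporting time window ending at Day 210 already means the 6-month report stops there, and that the 12-, 18- and 24-month values belong to the final report. Sections 5.3.4 and 5.3.5 support this: each lists times out to 24 months and then limits the 6-month report to Day 210, so such a list can cover both reports. Separate table shells (Appendix 1.1 and 1.2) and a derived data specification (Appendix 2) exist but are not in the supplied text, and they may settle what is printed. The endpoints are also exploratory and may not be reported at all (CIP 7.6).

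Much of this stands. The late values appear only if the 6-month output goes past Day 210, and a drafting omission is the likeliest explanation. It does not clear the text, though. Sections 5.3.7 and 5.3.10.1 lack the limiting sentence that 5.3.4 and 5.3.5 carry. If the tables did stop at Day 210, the event rule would still count later failures beside non-events cut at Day 210.

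A reader might infer that 5.3.8 shares the fault in full. The documents do not support that: its event comes from 5.2.4, which limits the abandonment date to a specific visit, so what needs attention there is the list of 12- to 24-month times. A reader might equally take 5.3.4 and 5.3.5 as sound models. They are sound on the reported rate, but their event rule is uncapped too.

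**Conclusion.** The point holds for primary patency and time to CVC removal in the 6-month report. Followed as written, the rule makes censoring depend on outcome after Day 210. For primary patency the 12-month value would be about 24% where actual follow-up gives 52% to 61%, and the 24-month value would be 0%. About 11 to 21 of 52 to 62 counted events would lie beyond the censoring horizon. These sizes rest on the 72.4% anchor, the plan's attrition and enrollment assumptions, and the assumed Weibull shapes. The fall to zero after the last late failure does not depend on the shape.

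Two stronger conclusions are tempting and unsupported. The first is that the 6-month patency estimate is wrong: every estimate up to Day 210 is the same under either rule. The second is that the final report or the trial's main conclusions are compromised: Day 760 is the end of the 24-month window, so the final report is essentially unaffected, and no primary or secondary endpoint, hypothesis test or sample size depends on these curves. It also does not reach every event-free participant, because PD, transplant, access discontinuation or study discontinuation before Day 210 is censored earlier.

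**What to change.** State one horizon for events, censoring and counts in the 6-month report, by either route:

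- **(a) Stop at Day 210.** Count only events on or before Day 210. Censor everyone else, including later failures, at Day 210 or at last follow-up if earlier. Present only times through 6 months.
- **(b) Use actual follow-up.** Censor event-free participants at the earlier of last available follow-up and the data cutoff, keeping the existing earlier censoring events, and present later times on that basis.

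Apply the chosen route consistently: 5.3.7 and 5.3.10.1 need the full change. Under (a), 5.3.8 needs its 12- to 24-month times assigned to the final report, and 5.3.4 and 5.3.5 need their event counts capped at Day 210. Then check that the Appendix 1.1 shells and the Appendix 2 derivations agree.

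The cost is about one SAP sentence per section and one change to the derived censoring date or event flag. No new data are needed. Route (a) matches the matched-horizon wording the SAP already uses in 5.1.1 and 5.3.9.

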#### **5.3.8** Cumulative Patency

The time interval for cumulative patency is defined as the time from HD AV access creation to access abandonment.

Kaplan-Meier (KM) analysis will be used to estimate the time interval of cumulative patency. The following definition will be applied:

- If permanent abandonment (as detailed in Section 5.2.4) occurs, the participant is considered as having the event (loss of cumulative patency), and the corresponding abandonment date will be used in the analysis.
- If the participant was as transferred to PD, or had a kidney transplant, or had access discontinuation, or discontinued before the end of a specific visit window (e.g., Day 210 for 6-month visit) without the event, the participant is considered as censored at the earliest date among these events (i.e., PD start date, kidney

transplant date, date of access discontinuation, last date of available study data including the unscheduled visit date).

• Otherwise, if the participant is still in the investigation without the event and has passed a specific visit by the cutoff date of database lock, the participant will be censored at the end of the reporting time window (e.g., 180+30 = Day 210 for the 6-month reporting, 730+30 = 760 for the 24-month reporting) for this analysis.

This endpoint will be evaluated on the AT population. The number of participants with events, number of participants censored, time to event (days), and proportion of participants with event free along with the 95% CI will be presented at 6-, 12-, 18-, and 24-months post creation using the KM method.

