4.4 Applicable Endpoint Definitions

Access Abandonment (permanent abandonment) is defined as the point at which the access can no longer be used for one or two needle prescribed HD as it may be unable to provide adequate flows and / or is deemed unsafe for the participant, and the associated problem cannot be corrected by any further intervention, including medical, surgical, or endovascular interventions or rest.^{8,19} Participants with an abandoned index AVF will continue with follow-up through 24-months and data will be collected on safety and interventions.

A HD AV access is not considered abandoned:

- If the participant discontinues use of the AV access due to kidney transplant, initiation of PD, or participant preference.
- During the maturation period or while waiting for a second stage procedure unless the principal investigator (PI) determines the participant requires and they then receive an alternative HD vascular access.

- During planned interventions, including transposition.
- If all reasonable efforts have not been attempted (and documented) to improve the condition of the access for it to be used.

A discontinuation of use of the clinical investigation AVF for any reason that does not meet this definition of access abandonment will be considered a temporary interruption.

Access Circuit Censoring Events include participant transfer to PD, kidney transplantation or the event of a participants premature discontinuation in the investigation due to withdrawn consent, withdrawal by PI, Lost to Follow-Up (LTF), or participant death (refer to Section 6.5 for definitions).

Adjunctive Procedure(s): Procedure(s) completed during the index procedure (prior to leaving the procedure room) as part of Standard-of-Care (SOC) procedures. These may include procedures to facilitate maturation and / or cannulation of the AVF, procedures to maintain use of the AVF, procedures to ensure HD continuity, as well as procedures to address AFs.

Second Stage Procedure(s): Facilitation Interventions (as defined below) intended to support the cannulation of arterialized vein segments that are determined to be needed a priori to or at the time of the index procedure (i.e. pre-planned facilitation interventions intended to support cannulation). Second stage procedures will not count against the intervention or patency endpoints and will require completion of the Second Stage Procedures eCRF.

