## 2.7 Endpoints

Note: The term access abandonment is synonymous with permanent abandonment for the purposes of these investigation documents. Access abandonment (permanent abandonment) is an abandonment that meets the definition in Section 4.4 of the CIP. The term access discontinuation is used to refer to any discontinuation of use of the access that does not meet these criteria of the definition and may also be referred to as a "temporary interruption" as per the CIP.

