- Otherwise, if the participant did not achieve physiological maturation and has passed the specific visit
  window by the cutoff date of database lock, the participant is considered as not having an event. If the
  participant had access permanent abandonment prior to achieving physiological maturation and has passed
  the specific visit window by the cutoff date of database lock, the participant is considered as not having an
  event.

This endpoint will be evaluated on the AT population. The proportion of physiological maturation and the 95% two-sided CI will be provided using the Clopper-Pearson method. For the 6-month reporting, the physiological maturation rate up to 6-months (up to Day 210) will be presented. For the final reporting, the physiological maturation rate up to 24-months (up to Day 760) will be presented.

Similar analysis will be done for exploratory purposes, for physiological maturation defined as an AVF having at least 500 mL / min of flow in the brachial artery and an outflow vein diameter of  $\geq$  5 mm as measured by DUS.

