#### 5.2.3 Cannulation Success

Cannulation success is defined as with successful first use for HD using 2-needle cannulation. This endpoint will be evaluated through 6 months. Additionally, for exploratory purposes, the endpoint will be evaluated through 30 days, 6 weeks, 3 months, 12 months, 18 months, and 24 months.

The event of cannulation success will be identified if:

On the EndoAVF Dialysis page, "Date endoAVF First Used with 2 Needles for Hemodialysis" is not NULL and within a specific visit (e.g., within 210 days for 6 months post creation).

Kaplan-Meier (KM) analysis will be used to estimate the time from HD AV access creation (the date of index procedure) to first successful use for HD using 2-needle cannulation through certain post creation visit.

- If cannulation success occurs, the participant is considered as having the event at the corresponding date.
- If the participant was transferred to PDs, or had a kidney transplant, or had access discontinuation, or discontinued before the end of a specific visit window (e.g.180+30 = Day 210 for 6-month visit) without cannulation success, the participant is considered as censored at the earliest date among these events (i.e. PD start date, kidney transplant date, date of access discontinuation, or last date of available study data including the unscheduled visit date).
- Otherwise, if the participant did not achieve cannulation success and has passed the specific visit window by the cutoff date of database lock, the participant will be censored at the end of the reporting time window (e.g., 180+30 = Day 210 for the 6-month reporting, 730+30 = 760 for the 24-month reporting) for this analysis. If the participant had access permanent abandonment prior to achieving cannulation success and has passed the specific visit window by the cutoff date of database lock, the participant will be censored at the date of permanent abandonment.

This endpoint will be evaluated on the AT population. The number of participants with events, number of participants censored, time to event (days), and proportion of participants with events along with the 95% CI will be presented at 6-months post creation using the KM method. For the 6-month reporting, the cannulation success rate up to 6-months (up to Day 210) will be presented. For the final reporting, the cannulation success rate up to 24-months (up to Day 760) will be presented.

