#### **5.2.4** Cumulative Functional Patency

The time interval of cumulative functional patency is defined as the time from first successful HD AV access use for HD using 2-needle cannulation to access abandonment. This endpoint will be evaluated through 12-months. Additionally, for exploratory purposes, the endpoint will be evaluated through 6 months, 18 months, and 24 months.

Only the participants who have started 2-needle HD using the endoAVF will be considered as evaluable for this endpoint.

Access Abandonment (Permanent Abandonment) will be identified if:

On the EndoAVF Dialysis page, Date endoAVF Successfully Used with 2 Needles for Hemodialysis is not NULL and within a specific visit (e.g., within 395 days for 12 months).

and

On the EndoAVF Abandonment page, Date of Abandonment is not NULL and within a specific visit (e.g. within 395 days for 12 months), the question of "All Possible Attempts Have Been Made to Improve the Condition of the Access" is checked as Yes, and the question of "Could Further Endovascular Interventions

Salvage the Access" is checked as No, and the question of "Could Further Surgical Revisions Salvage the Access?" is checked as No, and Reason for Abandonment is selected as "The Access is No Longer Viable" or "The Access is Viable but there are Complications that Require the Abandonment of the Access".

The binary definition for cumulative functional patency is shown as below:

- If permanent abandonment, as detailed above, occurs on, or before, a specific visit (e.g., 365+30 = Day 395 for 12 months post creation), the participant is considered as having an event (loss of cumulative functional patency).
- If the participant was transferred to PD, or had a kidney transplant, or had access discontinuation, or discontinued before the beginning of a specific visit (e.g., 365-30 = Day 335 for 12 months post creation) without permanent abandonment, the participant is considered not evaluable and will not be included in the analysis.
- Otherwise, if the participant did not have permanent abandonment and has passed the specific visit window by the cutoff date of database lock, the participant is considered as not having an event.

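### Cumulative patency (SAP 5.3.8, exploratory) borrows an event rule that requires prior 2-needle use, so fistulas abandoned before use would be censored as event-free

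*SAP*

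**What the plan says.** SAP 5.3.8 defines cumulative patency as time from access creation to access abandonment, analysed by Kaplan-Meier in the full As-Treated (AT) population. Its event rule is a cross-reference: "If permanent abandonment (as detailed in Section 5.2.4) occurs, the participant is considered as having the event (loss of cumulative patency". Participants without the event are censored at PD transfer, transplant, access discontinuation or study discontinuation. Those still followed are censored at Day 210 (6-month reporting) or Day 760 (24-month reporting).

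SAP 5.2.4 (cumulative functional patency, timed from first 2-needle use) lists two conditions for permanent abandonment, joined by a stand-alone *and*:

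- on the EndoAVF Dialysis page, "Date endoAVF Successfully Used with 2 Needles for Hemodialysis is not NULL and within a specific visit";
- on the EndoAVF Abandonment page, an abandonment date, confirmation that the access cannot be salvaged, and one of two listed reasons.

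The same section says "Only the participants who have started 2-needle HD using the endoAVF will be considered as evaluable for this endpoint".

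Elsewhere abandonment carries no such condition. SAP 2.7 states "Access abandonment (permanent abandonment) is an abandonment that meets the definition in Section 4.4 of the CIP". SAP 5.3.7 (primary patency) begins its rule "Access Abandonment (Permanent Abandonment): on the EndoAVF Abandonment page" and uses that page alone. Protocol 4.4 allows abandonment during the maturation period once the investigator finds that an alternative access is required and the participant receives it.

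**The concern.** A first-use condition suits an endpoint whose clock starts at first use. It does not suit one whose clock starts at creation, because a fistula lost before it is ever used is a failure that cumulative patency is meant to count. If the cross-reference is programmed as written, those failures leave the numerator while the participants stay in the risk set.

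Primary and cumulative patency share a start date and a population, yet they would rest on two meanings of permanent abandonment. A pre-use abandonment would be a failure on one curve and event-free on the other. Protocol 2.1.2 reports cumulative patency among the device's main prior results, so an inflated figure is likely to be compared with it.

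**Working it through.** **1. Tracing a pre-use abandonment through 5.3.8**

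| Step | Source | Result |
|---|---|---|
| 2-needle use date is NULL | SAP 5.2.4, first condition | Condition fails |
| Abandonment-page criteria met | SAP 5.2.4, second condition | Condition holds |
| Conditions joined by *and* | SAP 5.2.4 | Not a permanent abandonment under 5.2.4 |
| Event rule cites 5.2.4 | SAP 5.3.8 | No event |
| "Participants with an abandoned index AVF will continue with follow-up through 24-months and data will be collected on safety and interventions" | Protocol 4.4 | Participant remains in follow-up |
| Access discontinuation is reserved for cases that do not meet Protocol 4.4 | SAP 2.7 | That censoring rule should not apply |
| Remaining rule | SAP 5.3.8, last bullet | Censored event-free at Day 210 or Day 760, or at last data if the participant leaves early |

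**2. Whether the SAP expects such cases**

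It does. SAP 5.2.3 provides for them: "If the participant had access permanent abandonment prior to achieving cannulation success". Section 5.2.2 has a parallel clause for a case where the "participant had access permanent abandonment prior to achieving physiological maturation". The 5.2.3 clause is the direct evidence; if the 5.2.4 definition were applied there, it would describe nobody.

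The cross-references also look interchanged. Section 5.3.9 (primary functional patency, timed from first use) points to the unconditioned rule in 5.3.7. Section 5.3.8 (timed from creation) points to the conditioned rule in 5.2.4.

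**3. Size**

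The plan gives no figure to reproduce. Inputs:

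- S = 0.773, the pooled 6-month cumulative patency in Protocol 2.1.2, used as an illustrative true value. The prior studies' definitions are not stated.
- f, the share of permanent abandonments before 2-needle use. It is not in the documents and is varied here.
- n = 150 treated participants. Expected abandonments without attrition: 150 × (1 − 0.773) = 150 × 0.227 ≈ 34.

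Reading A (the literal 5.3.8 rule; the participant stays at risk to Day 210): reported = 1 − (1 − f) × 0.227.

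Reading B (pre-use abandonments censored at the abandonment date, with proportional hazards): reported = 0.773^(1 − f).

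| f | Events missed (f × 34) | Reading A | Excess (points) | Reading B | Excess (points) |
|---|---|---|---|---|---|
| 0 | 0 | 77.3% | 0 | 77.3% | 0 |
| 0.25 | 8.5 | 83.0% | 5.7 | 82.4% | 5.1 |
| 0.5 | 17 | 88.7% | 11.4 | 87.9% | 10.6 |
| 0.75 | 25.5 | 94.3% | 17.0 | 93.8% | 16.5 |
| 1 | 34 | 100% | 22.7 | 100% | 22.7 |

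For scale, the binomial standard error at n = 150 without attrition is √(0.773 × 0.227 / 150) = 0.034, or 3.4 points. The bias exceeds it already at f = 0.25.

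**4. Simulation checks with attrition**

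- Reading A with 20% attrition by month 6 (the Protocol 7.3 assumption), pre-use abandonment uniform on days 30–120 and post-use on days 90–209, gave 82.9%, 88.6% and 94.3% at f = 0.25, 0.5 and 0.75, against a true 77.2–77.4%.
- A separate simulation (n = 150, 20% attrition, 300 replicates, pre-use abandonment on days 20–200, post-use on days 100–209) took 17.7% abandoned before use and 5% of the remainder after. The 5.3.7 definition gave 78.6%, Reading A 96.1% and Reading B 95.5%.
- In that second simulation, with all losses before use, the literal rule reported 100% at every loss rate tried (5%, 10%, 15%, 22.7%).

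**The case against.** The strongest reply is that the intent is plain. SAP 2.7 defines abandonment for all endpoints by reference to Protocol 4.4, SAP 2.7.3.10 repeats it for cumulative patency, and 5.3.7 sets out the page criteria just before 5.3.8. A sensible programmer may read the cross-reference as meaning only the abandonment-page detail, and Appendix 2, which was not available, may already specify this. All of that supports the correction. It does not make the written event rule right.

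Three narrower points have some force:

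- **Censoring date.** Reading A relies on SAP 2.7 to rule out access discontinuation, yet the same note, if it governs, would make the case an event. If 5.2.4 overrides it, censoring at the abandonment date is arguable, and SAP 5.3.14 identifies abandonment and discontinuation from one page. The date is therefore not firmly settled. Both routes are event-free, and they differ by less than one point in the table.
- **Sections 5.2.2 and 5.2.3.** The 5.2.2 clause is weak evidence: a fistula could be used once with two needles and abandoned without meeting the maturation criteria. Section 5.2.3 does not itself cite 5.2.4, so it shows that pre-use abandonment is foreseen, not a formal clash.
- **Size.** f is unknown. Protocol 2.1.2 pairs 77.3% cumulative patency with 100% functional patency among users, which suggests a high f if the definitions match. Protocol 2.1.1 reports one abandonment after a cannulation injury without saying whether successful 2-needle use came first. Neither fixes f, and f = 1 should not be assumed.

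The endpoint is exploratory, and Protocol 7.6 allows it to go unreported. That limits the consequence but leaves the error in place.

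**Conclusion.** The concern holds for the SAP text. As written, 5.3.8 cannot count a fistula abandoned before 2-needle use as a loss of cumulative patency, which contradicts the endpoint's definition in both documents. The estimate is biased upward whenever such abandonments occur and the rule is programmed literally. With a true value of 77.3%, the excess is about 5 to 17 points for f between 0.25 and 0.75 under either censoring reading. These figures illustrate the range and do not predict the result, because f and the prior studies' definitions are not given.

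The effect is confined to this exploratory endpoint. The primary endpoints, the secondary functional patency endpoint among users, alpha and power are untouched. Pre-use abandonments still count as failures in primary patency and, if they precede maturation, as non-events in physiological maturation. Whether the bias would reach the report depends on the derived-data specification in Appendix 2.

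**What to change.** In SAP 5.3.8, replace the reference to 5.2.4 with the EndoAVF Abandonment page criteria in 5.3.7 (equivalently Protocol 4.4), and state that no 2-needle use date is required.

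As a minor clarification in 5.2.4, move the 2-needle date out of the abandonment rule and keep it only as the evaluability rule that section already states. Reconcile this with the separate full-AT run described there, which is redundant once the evaluability rule is applied.

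Check the abandonment flag in Appendix 2 against the corrected text before database lock. The cost is one cross-reference, one sentence and one check of a derived variable, with no new data and no change to sample size or testing.
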